The ICD clearly states additional costs: You do not have to pay for the specific study supplements. Since these same tests would be conducted as part of the routine care for macular degeneration, they would be submitted to your insurance plan and you will be responsible as usual, for expenses under deductibles and copays.

LUMEGA-Z

Ingredients

Serving Size: 0.75 FL. OZ. (1.5 Tbsp)	Servings Per Container: 7	
Amount Per Serving 0.75 FL. OZ.		% Daily Value
Calories	10	
Vitamin C (as ascorbic acid and calcium ascorbate)	500 mg	833%
Vitamin D3 (as cholecalciferol MCT)	2000 IU	500%
Vitamin E (as mixed tocopherols with not less than 50 mg of gamma tocopherol)	200 IU	665%
Thiamin (vitamin B1 as thiamin HCl)	1.5 mg	100%
Riboflavin	1.7 mg	100%
Niacin (as niacinamide)	20 mg	100%
Vitamin B6 (as pyridoxine HCl)	10 mg	500%
Folate (as folic acid)	800 mcg	200%
Vitamin B12 (as methylcobalamin)	1000 mcg	16,667%
Biotin	100 mcg	33%
Pantothenic Acid (as d-calcium pantothenate)	10 mg	100%
Calcium (as calcium lactate gluconate)	250 mg	25%
Magnesium (as magnesium citrate)	100 mg	25%
Zinc (as zinc amino acid chelate)	25 mg	167%
Selenium (as selenium sodium selenite)	70 mcg	100%
Copper (as copper gluconate)	2 mg	100%
Manganese (as manganese gluconate)	2 mg	100%
Chromium (as chromium picolinate)	120 mcg	100%
Molybdenum (glycinate chelate)	75 mcg	100%
NAC (N-acetyl-cysteine)	500 mg	*
Acetyl-L-Carnitine	500 mg	*
L-Taurine	500 mg	*
Quercetin	100 mg	*
CoQ10 (as ubiquinone)	50 mg	*
Lutein**	15 mg	*
Meso-zeaxanthin**	10 mg	*
Zeaxanthin**	3 mg	*
Astaxanthin	1000 mcg	*
Lycopene	500 mcg	*
Proprietary Ocular Antioxidant Blend (bilberry fruit extract 4:1, alpha-lipoic acid)	200 mg	

* Daily value not established.

Other Ingredients: Purified water, vegetable glycerin, polysorbate 80, acacia gum, soybean lecithin, malic acid, natural flavors, sucralose, potassium sorbate, sodium benzoate, medium chain triglycerides.

**Contains *Nutri-Mz* and sold subject to US patents 6,218,436 and 6,329,432 and others worldwide.

NO sugar, yeast, gluten, or dairy.

Omega Boost

Ingredient Facts

Serving Size: 2 Soft Gels	Servings Per Container: 30	
Amount Per Serving		% Daily Value*
Calories	10	
Calories from Fat	10	
Total Fat	1.5 g	2%
Saturated Fat	0 g	0%
Polyunsaturated Fat	1 g	†
Monounsaturated Fat	0 g	†
Fish Oil Concentrate	1260 mg	†
DHA (docosahexaenoic acid)	620 mg	†
EPA (eicosapentaenoic acid)	160 mg	†

* Percent Daily Values are based on a 2,000 calorie diet.

† Daily value not established.

Ingredients: Alaska Walleye Pollock (*theragra chalcogramma*), gelatin, glycerin, purified water, mixed natural tocopherols.

NO gluten, dairy, or artificial colors or flavors.

Each 4-week supply includes:

4 bottles x 5.25 Fl. Oz.

Lumega-Z Medical Food

With 60 Omega Boost Soft Gels

LUMEGA-Z®
Advanced Ocular Health
Medical Food

The Medical Food created
to restore and maintain the
Macular Pigment

LUMEGA-Z®
Advanced Ocular Health
Medical Food

Contains all three
macular carotenoids:

Lutein

Zeaxanthin

Meso-zeaxanthin

as well as a robust complex
of critical Micronutrients and
Omega 3's

GUARDION®
HEALTH SCIENCES
The Macular Pigment Specialists

Formulated and distributed by:
Guardion Health Sciences, Inc.
San Diego, California

[figure not shown]
Made in the U.S.A.

Patent Pending

[figure not shown]
What is Lumega-Z?

Lumega-Z is a medical food created to restore and maintain the macular protective pigment.

Macular pigment protects the macula (the part of your retina responsible for sharp, central vision) against oxidative stress, free radicals, and damaging blue light.

Example of a depleted macular pigment

[figure not shown]

Example of a restored macular pigment

A depleted macular pigment is a known high risk factor for age-related macular degeneration and other retinal diseases.

[figure not shown]
What is Medical Food?

A Medical Food is not a drug. It is not a supplement either.

Medical foods are a regulated category of product "... formulated to be consumed or administered... under the supervision of a professional healthcare provider and intended for the specific dietary management of a disease or condition for which distinctive nutritional requirements, based on recognized scientific principles, are established by medical evaluation."

(Per Section 5(b) of the Orphan Drug Act)

LUMEGA-Z®
Advanced Ocular Health
Medical Food

Restores and maintains a depleted macular pigment

Decreases glare and light sensitivity

Liquid formula is easy to swallow and digest

Promotes overall ocular health

Can replace your daily multivitamin

Able to be purchased with Healthcare Flexible Spending Account (FSA)

Tax-deductible as a medical expense

All research and scientific data is available upon request.

PreserVision AREDS 2 Formula Eye Vitamins for AMD

[name]

Thu 10/26/2017 11:32 PM

To: [name] <[contact]>;

[figure not shown]
Cc: [name] <[contact]>;

Sunday, October 15, 2017
4:26 PM

[name] • P: [contact] • F: [contact] • [contact]

SPONSOR: GUARDIAN HEALTH SCIENCES **PROTOCOL #:** 1 **VERSION:** 2 **27 DEC 2017**

INVESTIGATOR NAME: [name].

A. REPORTING GUIDELINES:

If you are not familiar with Salus IRB reporting requirements regarding unanticipated problems (UPs), deviations, and other safety information, refer to the guidance document, "Reporting Guidelines For Unanticipated Problems, Deviations, and Other Safety Information," on the Salus IRB website.

Reports that must be submitted are those reports that indicate a new or increased risk of harm to research participants or others. Generally, to be reportable such an event should be unknown to the IRB and requires an action taken to minimize the risk to participants. For example, a safety-related change to the protocol, additional disclosure of risk in the consent form or IRB, or other corrective action.

If you are required by your site or sponsor policy to submit IND Safety, MedWatch, SUSAR, or CIOMS Reports, or other safety information that does not meet the definition of an unanticipated problem and, therefore, does not require reporting to Salus IRB, use this form.

Salus IRB does not require reporting of minor protocol deviations. If you are required by your site or sponsor policy to submit minor protocol deviations, use this form.

For those events that Salus IRB does not require to be reported, if in the PI's judgment, any adverse events, minor protocol deviations or other events, when considered together indicate that changes to the research plan and/or consent form should be made, then the PI should provide an analysis of the events and any rationale for suggested changes at the time of continuing review, interim review, and/or site closure.

B. REPORT TYPE:

- Minor Unplanned Protocol Deviation – is defined as an accidental or unintentional deviation from the Salus IRB-approved protocol that did not involve a new or increased risk to one or more research participants, did not adversely affect the rights, safety, or welfare of one or more participants, and did not adversely affect the conduct of the study.

Examples are: participant missed visit due to holidays, participant failed to return diary, participant failed to initial every page of the consent form, or other deviations that involve only logistical issues or only affect administrative aspects of the study.

[name] • P: [contact] • F: [contact] • [contact]

SPONSOR: GUARDIAN HEALTH SCIENCES **PROTOCOL #:** 1 VERSION 2 27 DEC 2018
INVESTIGATOR NAME: [name].

A. REPORTING GUIDELINES:

If you are not familiar with Salus IRB reporting requirements regarding unanticipated problems (UPs), deviations, and other safety information, refer to the guidance document, "Reporting Guidelines For Unanticipated Problems, Deviations, and Other Safety Information," on the Salus IRB website.

Reports that must be submitted are those reports that indicate a new or increased risk of harm to research participants or others. Generally, to be reportable such an event should be unknown to the IRB and requires an action taken to minimize the risk to participants. For example, a safety-related change to the protocol, additional disclosure of risk in the consent form or IB, or other corrective action.

If you are required by your site or sponsor policy to submit IND Safety, MedWatch, SUSAR, or CIOMS Reports, or other safety information that does not meet the definition of an unanticipated problem and, therefore, does not require reporting to Salus IRB, use this form.

Salus IRB does not require reporting of minor protocol deviations. If you are required by your site or sponsor policy to submit minor protocol deviations, use this form.

For those events that Salus IRB does not require to be reported, if in the PI's judgment, any adverse events, minor protocol deviations or other events, when considered together indicate that changes to the research plan and/or consent form should be made, then the PI should provide an analysis of the events and any rationale for suggested changes at the time of continuing review, interim review, and/or site closure.

B. REPORT TYPE:

1. Minor Unplanned Protocol Deviation – is defined as an accidental or unintentional deviation from the Salus IRB-approved protocol that did not involve a new or increased risk to one or more research participants, did not adversely affect the rights, safety, or welfare of one or more participants, and did not adversely affect the conduct of the study.

Examples are: participant missed visit due to holidays, participant failed to return diary, participant failed to initial every page of the consent form, or other deviations that involve only logistical issues or only affect administrative aspects of the study.

At the end of the trial period, data will be collected by the Principal Investigator and analyzed by professional optical engineers at Western University of Health Sciences, Pomona CA. The data provided will only contain patient ID, age, and sex, without containing any identifying details about each participant. Data will be analyzed upon measurement quality, according to the respective manufacturer procedures, in each outcome measure. In the event which data is missing or incomplete, we will evaluate the appropriate measures to include the available information and consult with qualified professionals.

Preliminary and sub-analyses will be performed using the statistical programming software, SPSS Systems. The objective is to examine the distribution and potential relationships within data sets through standardized descriptive-numerical summaries. Statistical analysis strategies may include a mixed-design Analysis Of Variance (ANOVA) to examine the following outcome measures across the three time-points of data collection; including visual acuity, contrast sensitivity, dark adaptation recovery, and MPOD levels. A post hoc sub-analysis of paired sample t-test may be used (either Bonferroni correction or Tukey test) to evaluate the change in each outcome measure parameter, if needed, in respect to each treatment group. Additionally, each group-measurement may be separated and analyzed by eye; to evaluate inter-eye differences from each treatment. Results of the statistical analysis will be analyzed as group averages of each outcome measurement.

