27 DEC 2017

Controlled Study of the Effect of a Medical Food
Containing All Three Macular Carotenoids and Essential Cofactors
Compared to AREDS2 on Early Macular Degeneration

PURPOSE:

This 6-month randomized control study is undertaken to compare the effect of treatment with LumegaZ, a medical food containing lutein, zeaxanthin, and meso-zeaxanthin, as well as essential cofactors, other antioxidants, and mitochondrial support, with the effect of treatment with AREDS2. Patients with early macular degeneration, defined as photographically visible drusen with or without abnormal dark adaptation on the AdaptDx will be randomized 2:1 and both groups will be compared to untreated patients with normal dark adaptation.

BACKGROUND:

Macular degeneration is the most common cause of blindness in people over the age of 60. The incidence of macular degeneration at all stages is 1 in 8 and is more common than diabetes and glaucoma at the same age.

The dietary carotenoids lutein and zeaxanthin (derived primarily from leafy green vegetables and other colored fruits and vegetables) as well as meso-zeaxanthin, a metabolite of lutein, are stored in the macula in all healthy retinas. This area serves central vision, and is the specific area that is affected by macular degeneration. The accumulation of these pigments results in a yellowish coloration of the retina, the concentration of which is called macular pigment density. A large multicenter trial called AREDS 2 (2013) showed that supplementing lutein and zeaxanthin reduced progression of moderate to advanced AMD by 25%. The CREST (2014) and MOST (2015) studies showed that supplementation of all 3 macular pigments resulted in normalization of the macular pigment profile and improvement in contrast sensitivity in early AMD. All 3 macular carotenoids are recognized by the FDA as 'generally regarded as safe (GRAS) for supplementation in foods.

Macular degeneration can be understood as a disease of excessive oxidation of the retinal tissue with genetic, age, dietary and light exposure components leading to accumulation of oxidized cholesterol and polyunsaturated fatty acids both on Bruch's membrane and between Bruch's membrane and the retinal pigment epithelium in a condition analogous to plaque

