buildup in arteries. These deposits block transfer of waste out of the retina leading to more accumulation and block transfer of nutrients into the retina. In macular degeneration, not enough Vitamin A crosses Bruch's membrane because of the build-up, causing a localized deficiency of Retinol in the parafoveal rods. This causes slower dark adaptation after bleaching light, which is the earliest symptom of macular degeneration: difficulty driving in darkness or adapting to dark conditions increasing with aging.

Abnormal dark adaptation found by AdaptDX testing is the earliest clinical sign of macular degeneration. This has enabled diagnosis of subclinical macular degeneration with 90% positive and negative test reliability, 3-5 years before the first drusen is visible clinically. Those patients who exhibit impaired dark adaptation, whether they are subclinical with no drusen or early with mild drusen, may benefit from nutritional and /or lifestyle changes which could significantly slow the progression of the disease. This would result in maintenance of retinal health and visual performance.

It is clear that early, effective intervention in any disease process is the key to reducing morbidity. Earlier diagnosis of macular degeneration is now possible with AdaptDX testing. Effective intervention involves reducing the photo-oxidative damage of the retina caused by the visual process in the retina, and potential clearing of the early stage blockage of bidirectional transport across Bruch's membrane. Thirty percent of people over age 60 have abnormal dark adaptation. Likewise, 30% of people have an abnormal spatial profile of macular pigment indicating insufficient meso-zeaxanthin creation from lutein. Supplementing meso-zeaxanthin as well as lutein and zeaxanthin can restore the macular pigment spatial profile and improve visual performance in early macular degeneration. Early results from an as yet unpublished exploratory study in progress with such supplementation in subclinical AMD indicate improvement in MPOD and best corrected contrast sensitivity in many patients by 6 months.

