A medical food is a special category of supplement approval by the FDA where physicians prescribe it for nutritional treatment of specific medical conditions. The medical food to be used by patients in this study contains not only all the macular carotenoids in micelle formulation for improved absorption, but also significant cofactors, such as vitamins, minerals, ALA, astaxanthin, N-acetylcysteine, carnosine and others. All of these ingredients working together should significantly improve the mitochondrial, antioxidant and anti-inflammatory functions of the retina. This should allow creation of less damage to critical elements of the retina and less toxic waste such as oxidized cholesterol and oxidized polyunsaturated fatty acids which are the major components of the sub-RPE and Bruch's membrane deposits. This controlled study will attempt to show that using a medical food designed to optimize retinal metabolism and antioxidant capacity will exert a positive effect in subclinical macular degeneration, which is greater than supplementation with AREDS2 and will also improve measured functions into the range of function in untreated normal patients.

STUDY:

All study candidates are routine patients in a general ophthalmology practice. All patients who are interested will be offered the opportunity to participate in this controlled study of the effect of a nutritional food on subclinical macular degeneration. Each patient will undergo a screening AdaptDx to separate patients with normal dark adaptation from those with abnormal dark adaptation. All patients will receive the same exams at baseline, 3 months and 6 months. For details, see the listing below. Those who are confirmed as normal with extended dark adaptation testing will receive no treatment precisely because they are defined as not having a problem needing this treatment. Those who are confirmed with early macular degeneration by photographically visible drusen and have dark adaptation scores of less than 10 minutes will receive treatment by ingesting a commercially available medical food, containing all 3 macular pigment as well as essential cofactors and other antioxidants, or AREDS2, randomized 2:1 for 6 months. If positive effects are noted, it is possible that the study might be extended. The tasks below are part of standard diagnostic clinical eyecare practice.

- Baseline, 3 month and 6 month examinations
 - History
 - Risk factors
 - Best corrected visual acuity

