 - Best corrected contrast sensitivity (CSV 1000)
 - Intraocular pressure, nondilated slit-lamp exam
 - Dark adaptation (AdaptDX, extended exam)
 - Macular pigment optical density (MapcatSF)
 - Macular ocular coherence tomography (Zeiss Cirrus OCT)
 - Fundus photography (Zeiss VisuCam Pro)

Because these patients will have additional problems found in routine clinical practice, other exams may occur for other problems and will not be considered part of the study data. Should any adverse effects be noted thought to be from the study treatment, the patient will be examined to understand the effect and if it is felt to be not significant, the patient will be asked to continue in the study. In the highly unlikely event a serious adverse effect is noted the patient will be terminated from the study and appropriate treatment will be undertaken.

DATA COLLECTION:

The data will be maintained on standardized forms and printable graphics, as well as in the patient's routine clinical file. To protect identifiable information, files will be locked in a file cabinet, accessible only the PI and the study coordinator. Data will be transcribed without

personally identifiable information into standard Excel files and analyzed as appropriate using standard statistical techniques.

STUDY REQUIREMENTS:

This study will be conducted with the protocol, good clinical practices and applicable regulatory requirements. This is a no significant risk study, using commercially available supplements, Lumega-Z or AREDS2, containing 2 or 3 of the three carotenoids that are FDA “generally recognized as safe” for food supplementation and are found in all healthy retinas. All examinations are noninvasive and are performed with FDA cleared, commercially available medical devices in routine clinical use.

The study population consists of 90 male and female patients in a routine clinical practice age 60 and over who have early macular degeneration as defined as a few drusen visible on Visucam and have an AdaptDx score less than or equal to 10 minutes. No vulnerable populations will be studied.

The patient will be studied for improvements in ocular function. Primary endpoints would be improvement in macular pigment optical density long form, improvement in best corrected contrast sensitivity and improvement in best corrected vision. Secondary endpoints would be improvement of AdaptDx long form time or a reduction in drusen.

The study supplements for each

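### The only between-arm method named pools one error variance across 2:1 arms, so its error rate and interval are not robust if the spread of change differs between arms (minor safeguard)

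*Combined protocol and SAP*

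**What the plan says.** The statistical analysis text, which stands without a heading at the end of the document, says "Statistical analysis strategies may include a mixed-design Analysis Of Variance (ANOVA". It applies this to visual acuity, contrast sensitivity, dark adaptation and macular pigment density "across the three time-points of data collection", using SPSS. The paired t-tests mentioned next look at change within each treatment group and do not compare the products.

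Under STUDY, eligible patients receive the medical food "or AREDS2, randomized 2:1 for 6 months". PURPOSE adds that patients "will be randomized 2:1 and both groups will be compared to untreated patients with normal dark adaptation". STUDY REQUIREMENTS gives the size: "The study population consists of 90 male and female patients".

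The documents name no check of variance homogeneity, no unequal-variance test, no robust standard error and no arm-specific covariance. They give no standard deviation for either arm, no significance level and no power.

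**The concern.** A mixed-design ANOVA estimates one error variance across all groups. With arms of equal size, a difference in spread between them barely affects the comparison of means. With 2:1 arms it does, because the larger arm dominates the pooled variance while the smaller arm dominates the true standard error of the difference.

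The consequence depends on which arm is more variable:

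- **Larger arm more variable:** the pooled standard error is too large, the interval too wide, and power is lost on the trial's main question.
- **Smaller arm more variable:** the standard error is too small, the interval too narrow, and the false-positive rate exceeds its nominal level, in favour of either product.

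**Working it through.** The plan has no figure of its own to reproduce: 90 is stated without a level, power, effect size or SD.

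**Inputs**

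- Arm sizes: n1 = 60, n2 = 30. This assumes that all 90 are randomised; the order of words under STUDY suggests, but does not state, that Lumega-Z is the larger arm.
- Level: two-sided 5% (assumed).
- r = SD of change in the larger arm divided by SD in the smaller arm (assumed and varied).
- Complete data (assumed).

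**Formulas**, with the smaller arm's SD set to 1:

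- Pooled SE² = [(59r² + 29)/88] × (1/60 + 1/30)
- True SE² = r²/60 + 1/30
- q = pooled SE / true SE
- Actual error = 2[1 − Φ(1.96q)]
- Power, where a correct SE would give 80%, = Φ(2.80 − 1.96q)

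**Worked case, r = 1.25.** Pooled SE² = [(92.19 + 29)/88] × 0.05 = 0.0689. True SE² = 0.0260 + 0.0333 = 0.0594. So q = √(0.0689/0.0594) = 1.08, and the actual error is about 3.5%.

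| Which arm is more variable | SD ratio | q | Actual error |
|---|---|---|---|
| Neither | 1 | 1.00 | 5.0% |
| Larger | 1.10 | 1.03 | 4.3% |
| Larger | 1.25 | 1.08 | 3.5% |
| Larger | 1.5 | 1.14 | 2.6% |
| Smaller | 1.25 | 0.93 | 6.9% |
| Smaller | 1.5 | 0.88 | 8.5% |

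Interval coverage is 100% minus the actual error: for example 93.1% for 6.9%, and 91.5% for 8.5%. When the larger arm is more variable, power falls from 80% to about 78% (ratio 1.10), 76% (1.25) or 72% (1.5).

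**Does the three-visit F test behave the same way?** The group-by-time F was simulated under no mean difference (20,000 runs; assumed change SDs 0.7 and 1.0 times the arm's scale, correlation 0.6, measurement noise SD 0.3). The Greenhouse-Geisser correction was applied, although the plan mentions none. It gave 3.2% and 6.7% at a ratio of 1.25, and 2.6% and 8.0% at 1.5, close to the closed form.

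**What removes the problem?** In 40,000 simulated trials per setting at 60 v 30, the Welch test on change stayed between 4.7% and 5.2% for SD ratios from 0.5 to 2. With 45 v 45 the corrected F stayed between 4.6% and 4.9%. The distortion therefore comes from unequal arm sizes combined with unequal spread.

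**Does the reading of 90 matter?** If the 90 include the untreated normals, an illustrative 40 v 20 gives nearly the same results (3.5% at ratio 1.25 with the larger arm more variable). If that third group enters the same ANOVA, its variance is pooled too.

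**The case against.** **No evidence of unequal spread.** This is the strongest objection, and it stands. A reader might infer from BACKGROUND that the Lumega-Z arm will be the more variable one. The text says that "30% of people have an abnormal spatial profile of macular pigment indicating insufficient meso-zeaxanthin creation from lutein", and reports from an unpublished exploratory study "improvement in MPOD and best corrected contrast sensitivity in many patients by 6 months", which suggests a mix of responders and non-responders. The documents do not support that conclusion. The 30% refers to people in general and to the pigment profile, not to response in acuity, contrast sensitivity or dark adaptation. The exploratory result says nothing about AREDS2. The same reasoning can also run the other way: if some people make too little meso-zeaxanthin from lutein, an arm given none may itself be a mixture, and supplying it directly could narrow the Lumega-Z spread.

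**Size under the responder argument.** If 30% respond by an extra d SDs, the variance rises by 0.3 × 0.7 × d². The SD ratio is √1.21 = 1.10 for d = 1 and √1.84 = 1.36 for d = 2. With Lumega-Z as the larger arm, actual error is then about 4.3% or 3.0%, and power about 78% or 74% instead of 80%. Both cases are conservative. The figures of 6.9% and 8.5% need the smaller arm to be more variable, and the documents do not show that it will be.

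**The ANOVA is only optional.** This is also true: the wording is permissive, and the lack of any firm between-arm test is the larger gap. But no alternative is named, so when the test is fixed the variance assumption should be fixed with it.

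**Conclusion.** The point holds as a conditional safeguard of minor weight. The named method is not robust to unequal spread under 2:1 allocation, and nothing in the documents allows for it. For SD ratios up to 1.25 in either direction, the actual error lies between about 3.5% and 6.9%; at 1.5 it is about 2.6% or 8.5%. These figures assume 60 v 30, a two-sided 5% level and complete data.

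A reader might infer that the trial's error rate is inflated, or that the comparison is biased towards one product. Neither follows: without SDs, neither the presence nor the direction of a variance difference can be established. The within-arm paired t-tests do not pool over arms and are unaffected.

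**What to change.** Add one sentence to the statistical analysis text: the Lumega-Z v AREDS2 difference in 6-month change and its 95% confidence interval will be estimated by the unequal-variance (Welch) method, not from the pooled ANOVA error term. If the sponsor adopts a baseline-adjusted model, the sentence should specify heteroscedasticity-robust standard errors instead. Settle which of the two applies before the data are examined, so that the choice adds no flexibility.

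Apply the same rule to the comparisons of each treated group with the untreated normals. That group is not randomised, and nothing in the documents suggests that its spread will match.

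The cost is one sentence and a routine analysis option. If the variances are in fact equal, simulation puts the loss at about half a percentage point of power (79.5% v 79.0%).

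### The only between-group model named, a three-visit mixed ANOVA, uses baseline as an outcome level; adjusting for baseline would estimate the 6-month Lumega-Z minus AREDS2 difference more precisely

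*Combined protocol and SAP*

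**What the plan says.** The unheaded statistical text at the end of the combined document names, as a possibility and not a commitment, one model that can compare groups: "a mixed-design Analysis Of Variance (ANOVA) to examine the following outcome measures across the three time-points of data collection". It lists the outcomes as "including visual acuity, contrast sensitivity, dark adaptation recovery, and MPOD levels". The STUDY section fixes the visits: "All patients will receive the same exams at baseline, 3 months and 6 months". Baseline is therefore one of the three levels of the repeated outcome.

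The only follow-up step named is optional and works within each treatment group: "A post hoc sub-analysis of paired sample t-test may be used (either Bonferroni correction or Tukey test) to evaluate the change in each outcome measure". No part of the documents mentions ANCOVA, a baseline covariate or a baseline-adjusted contrast between arms.

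The STUDY REQUIREMENTS section frames the endpoints as improvement: "Primary endpoints would be improvement in macular pigment optical density long form, improvement in best corrected contrast sensitivity and improvement in best corrected vision". The PURPOSE and STUDY sections describe 2:1 randomisation to Lumega-Z or AREDS2. They also describe a further, non-randomised comparison with untreated patients who have normal dark adaptation.

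**The concern.** Before treatment starts, the true difference between randomised arms is zero. A model that treats baseline as an outcome can yield a treatment effect in two ways.

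- **Group-by-time interaction.** This compares changes from baseline. It is valid, but it carries the full noise of the baseline measurement.
- **Group main effect.** This averages over all three visits, including the one at which no effect can exist, so the effect is diluted.

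Every outcome in the ANOVA is already measured at baseline. Using that value as covariate removes chance imbalance between the arms and reduces residual variance. What is at stake is precision in a trial whose comparator arm would have about 30 patients, and for which the documents give no power calculation showing that precision can be spared.

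**Working it through.** **Inputs from the documents.** Three visits at 0, 3 and 6 months (STUDY). Allocation 2:1 (PURPOSE, STUDY). Sample size: "The study population consists of 90 male and female patients in a routine clinical practice age 60 and over" (STUDY REQUIREMENTS).

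**Assumptions.** The documents give no alpha, effect size, SD, dropout rate or correlation. I assume that all 90 patients are randomised, hence 60 and 30; two-sided alpha of 0.05; complete data; equal variance at each visit and the same correlation r between any two visits; and a true 6-month difference of 0.5 SD. There is no figure in the plan to reproduce.

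**Step 1: dilution of a group main effect.** Let D be the 6-month difference.
- Constant effect from 3 months: (0 + D + D)/3 = two thirds of D.
- Linear growth: (0 + D/2 + D)/3 = half of D.

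**Step 2: variance of the 6-month contrast**, in units of SD² × (1/60 + 1/30) = 0.05 SD².
- Baseline as an outcome level (change score): 2(1 − r).
- Baseline as covariate (ANCOVA): 1 − r².
- Ratio: (1 − r²) / [2(1 − r)] = (1 + r)/2, which is below 1 for every r below 1.

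Example at r = 0.5: the change-score variance is 1.00 × 0.05, SE 0.224 SD; the ANCOVA variance is 0.75 × 0.05, SE 0.194 SD.

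**Step 3: results across r.** The fourth column is 90 × 2/(1 + r), the total that a change-score analysis needs to match ANCOVA on 90. Power is from the noncentral t distribution.

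| r | SE, change / ANCOVA (SD) | Variance ratio | Total to match | Power, change / ANCOVA |
|---|---|---|---|---|
| 0.3 | 0.265 / 0.213 | 0.65 | 138.5 | 46% / 64% |
| 0.5 | 0.224 / 0.194 | 0.75 | 120.0 | 60% / 72% |
| 0.7 | 0.173 / 0.160 | 0.85 | 105.9 | 81% / 87% |
| 0.8 | 0.141 / 0.134 | 0.90 | 100.0 | 94% / 96% |
| 0.9 | 0.100 / 0.097 | 0.95 | 94.7 | >99% / >99% |
| 0.95 | 0.071 / 0.070 | 0.975 | 92.3 | >99% / >99% |

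The like-for-like gain is therefore about 18, 12, 6 and 2 percentage points at r = 0.3, 0.5, 0.7 and 0.8, and negligible from 0.9 upward.

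**Step 4: simulation check** (60 v 30, 4,000 trials per scenario, 0.25 SD at 3 months and 0.5 SD at 6 months). The simulated variance ratios were 0.78, 0.86, 0.92 and 0.97 at r = 0.5, 0.7, 0.8 and 0.9, in line with (1 + r)/2. Power at r = 0.5 / 0.7 / 0.8:
- group main effect: 28 / 23 / 23%
- 2-df group-by-time interaction: 51 / 73 / 89%
- 6-month change score: 60 / 81 / 93%
- 6-month ANCOVA: 71 / 86 / 95%

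Only the step from change score to ANCOVA is due to how baseline is handled. The step from interaction to change score comes from replacing an omnibus test with a targeted contrast.

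**The case against.** The strongest reply has five parts.

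1. **The plan is not committed to this ANOVA.** Its wording is tentative. That stands, and the loss cannot be called certain. But this is the only between-group model named, and nothing else in the documents supplies baseline adjustment.
2. **The interaction test is valid.** That stands. Simulated type I error was 4.9 to 5.2% for all the methods compared. A reader might infer bias or an invalid test; the documents and the arithmetic show only lost precision.
3. **Nobody proposed the group main effect as the treatment test.** That also stands. The endpoints are worded as improvement and the follow-up tests concern change, both of which point to the interaction. A reader might take the 23 to 28% power as the plan's own; it applies only if the main effect were used.
4. **The interaction-to-ANCOVA gap overstates the case.** A reader might credit the whole of it (73 v 86% at r = 0.7) to baseline handling, but more than half of that is choice of contrast. If the full effect is present by 3 months, the interaction can even match a 6-month-only ANCOVA at high r (96% v 95% at r = 0.8). For the same quantity, adjustment remains more precise: for the mean of months 3 and 6 the variance ratio is 0.67 at r = 0.5 and 0.87 at r = 0.8.
5. **Baseline adjustment can mislead for the untreated group.** That stands. These patients are selected for normal dark adaptation and so differ at baseline by design. The adjustment must be confined to the randomised arms.

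**Conclusion.** The concern holds as one of precision. For the 6-month difference between the randomised arms, using baseline as covariate reduces variance by 35% at r = 0.3, 25% at 0.5, 15% at 0.7, 10% at 0.8, 5% at 0.9 and 2.5% at 0.95. The direction is secure for any r below 1 under the equal-variance assumption. The size is not, because r is undocumented and the gain may be small for a highly repeatable measure.

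The absolute power figures also rest on the assumed 0.5 SD and on the 60:30 split, which is inferred from 90 patients and 2:1 allocation. If fewer are randomised, power falls but the variance ratios do not change. A reader might infer that the planned analysis is wrong or that the trial will fail because of it; the documents support neither. The change is worth making because the baseline data will be in hand anyway.

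**What to change.** Replace the tentative ANOVA wording with a stated model for each continuous outcome:

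- Include the two randomised arms only.
- Use the 3- and 6-month values as outcomes, with arm, visit and arm-by-visit as factors.
- Use the baseline value of the same outcome as covariate, on the same eye or eye-average basis as the outcome.
- Report the adjusted Lumega-Z minus AREDS2 difference at 6 months with its 95% CI.
- Do not use a group main effect that includes the baseline visit.
- Compare the untreated normal group separately, without this baseline adjustment.

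The cost is a few lines of SAP text and slight extra analysis work. No new data are needed. The drawback is that the gain may be small where the measure is highly repeatable.
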